### Risks/Benefits:

The risks of C-RFA of the articular sensory branches of the knee are minimal. Sensory and motor testing of the target structure prior to lesioning reduces the risk of any neurologic injury and the motor nerves are not located at the planned lesion sites. Bleeding or infection can occur with any needle intervention.

Summary of Recruitment:

### 4.0 Data Analysis:

Primary outcome:

• Between-group difference in analgesic use (MQS III score) at 48 hours.

Secondary outcomes: Between groups at 48 hours, 1, 3, 6 months in:

- 1. Visual Analog Scale for pain (at rest, with mobilization or weight bearing)
- 2. Knee Society Scale (clinician); WOMAC (patient)
- 4. Physical therapy milestones
  - a. Time to active SLR
  - b. Time until patient can get out of bed
  - c. Time until patient able to ambulate < 100 feet
  - d. Time until patient able to ambulate around room > 100 feet

e. Time until patient is able to climb stairs (quantify specifics, how many steps are considered appropriate?)

- 5. Patient Global Perception of Change (GPC)
- 6. Patient Satisfaction (Likert scale)
- 6. Hospital Anxiety and Depression Score (HADI)
- 7. SF12
- 8. McGill Pain Questionnaire

9. Inpatient length of Stay (LOS; days) and Physical Therapy "clearance for discharge" (days)

- 10. Complications of the injection procedure
- 11. Medication related adverse events (i.e. sedation, nausea, pruritus, delirium)

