#### 1.0 Research Aims/Objective:

#### 1.1 Research Question(s):

Does Cooled Radiofrequency Ablation (C-RFA) of the articular sensory nerve supply to the knee prior to unilateral total knee replacement result in improved post-operative knee pain scores and decreased perioperative analgesic use as compared to standard perioperative medical therapy?

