## 3.0 Investigational Plan/Protocol Specifics

### General Design and Procedures.

This study design is a *prospective randomized trial* of C-RFA of 3 articular branches of the knee joint versus sham CRFA to examine the effects on post-operative opiate requirements during the first 48 hours after surgery (primary outcome). We will obtain approval from the Institutional Review Board at Northwestern University and will complete an informed consent process before initiating any study procedure.

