#### Participants

Inclusion criteria include:

- 1) Adults 30 to 80 years old
- 2) OA of the knee scheduled to undergo their first unilateral knee joint replacement
- 3) Willingness to undergo fluoroscopy-guided C-RFA or sham treatment.

Exclusion criteria include:

- 1) Conditions that preclude C-RFA or sham intervention (e.g. pregnancy, severe cardiac/pulmonary compromise; acute illness/infection; coagulopathy or bleeding disorder; allergic reactions/contraindications to a local anesthetic).
- 2) Prior TKR on either knee
- 3) Inability to write, speak or read in English
- 4) Patient refusal

Recruitment

Site(s) where study will be performed: Department of Anesthesiology, [name] Department of Orthopedic Surgery, [name] Patients who schedule a primary unilateral TKR with their orthopedic surgeon at NM will be asked to participate in the study by authorized research personnel. They will be screened to determine candidacy for the study; if they meet eligibility criteria, they will read and sign an informed consent form to participate. Each participant will be scheduled to see [name] in the Pain Medicine Center for the intervention procedure. They will be asked to be NPO for this visit and arrange a driver to accompany them home. This procedure will be performed 2-4 weeks prior to their planned knee surgery. The research assistant will calculate Morphine Equivalents (ME) of all analgesic medications including opiates, anti-inflammatories and membrane stabilizers.

Each participant will complete the following written outcome measures prior to the intervention: It will take approximately 10 minutes to complete the questionnaires.\* VAS pain score WOMAC questionnaire SF12 questionnaire Hospital Anxiety and Depression Inventory questionnaire McGill Questionnaire

Following the intervention procedure the following data points will be recorded: VAS pain score PGIC Questionnaire Patient satisfaction

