## Statistical Power

The power analysis for this study was performed using data from Choi et al and assumptions regarding perioperative opiate requirements in patients undergoing TKR without an indwelling epidural catheter or peripheral nerve block. A sample size of 28 per group is needed to detect a difference in analgesic use of 15 morphine equivalents (ME) per 24 hour cycle, assuming the controls use 47 ME per 24 hours cycle with a standard deviation of 19 ME with a power of .81 at alpha = 0.05. The sample size calculation was computed using a two-sided Mann-Whitney Test (PASS). To correct for lost to follow up and dropout rates, we will recruit 30 patients into each treatment group.

Duration of follow-up This trial is designed with 6-month duration of follow up after surgery.

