### 4.2 Interpretation of Anticipated Results:

## Statistical analysis

Means and standard deviations of participant demographic data, as well as mEQ, VAS, and other outcome scores will be calculated. Two tailed paired t tests will be used for parametric data; Wilcoxon rank sum tests will be used for non-parametric data in order to compare differences in outcome measures between the two treatment groups.

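### The protocol names two different primary outcomes (opiate requirements over 48 hours, and an MQS III analgesic score), and the power calculation is on a third scale, morphine equivalents per 24 hours

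*Combined protocol and SAP*

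**What the plan says.** The primary outcome is stated in two places, both current text.

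- **Section 3.0, General Design and Procedures:** the trial is "to examine the effects on post-operative opiate requirements during the first 48 hours after surgery (primary outcome"). No measurement scale is named.
- **Section 4.0, Data Analysis, under Primary outcome:** "Between-group difference in analgesic use (MQS III score) at 48 hours".

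Other sections bear on what is measured.

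- **Statistical Power:** the sizing rests partly on "assumptions regarding perioperative opiate requirements in patients undergoing TKR", but the target is to "detect a difference in analgesic use of 15 morphine equivalents (ME) per 24 hour cycle". Controls are taken to average 47 ME a day, the SD is put at 19 ME, and the claimed power is 0.81. The sizing test is a two-sided Mann-Whitney at alpha 0.05, with 28 per group needed and 30 recruited.
- **Section 4.2, Statistical analysis:** "Means and standard deviations of participant demographic data, as well as mEQ, VAS, and other outcome scores will be calculated". The abbreviation mEQ is not defined and MQS III is not mentioned.
- **Recruitment text under Participants:** the research assistant will "calculate Morphine Equivalents (ME) of all analgesic medications including opiates, anti-inflammatories and membrane stabilizers". This is the only place that says which drugs enter an ME figure.
- **Section 1.1, Research Question:** asks about "decreased perioperative analgesic use as compared to standard perioperative medical therapy", which is wider than opiates.

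**The concern.** The two statements of the primary outcome differ in the drugs covered (opiates; analgesics) and in the measure (none named; MQS III). On a literal reading they also differ in timing (over 48 hours; at 48 hours). The plan gives no rule for choosing between them.

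Two things are at stake. First, the primary outcome decides whether C-RFA is judged to have worked. If the choice is still open when data are unblinded, it can follow the results, and the two-sided 0.05 level then no longer protects the primary claim. Second, the stated power belongs to ME per 24 hours. If section 4.0 governs, the primary outcome has no power calculation. If section 3.0 governs, it inherits the stated power only if the ME inputs are opioid figures, which the plan does not say.

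**Working it through.** **Step 1. Reproduce the plan's figure.** Inputs from Statistical Power: difference 15 ME, SD 19 ME, 28 per group, two-sided alpha 0.05, Mann-Whitney test.

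- Standardized effect: d = 15/19 = 0.789.
- Effective size per arm for a Mann-Whitney test on normal data: m = n × 3/π = 28 × 0.955 = 26.74.
- Degrees of freedom: 2m − 2 = 51.5. Noncentrality: d × √(m/2) = 0.789 × √13.37 = 2.89. Critical t: 2.007.
- Power from the noncentral t: **0.8085**, against a stated 0.81. At 30 per arm: 0.8354.
- A simulation of the Mann-Whitney test with normal data (20,000 runs) gives 0.799 at 28 per arm.

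The stated figure reproduces on the ME scale.

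**Step 2. Try the same for MQS III.** The calculation needs a target difference and an SD, or their ratio. The documents give neither, and no conversion from ME. Power on MQS III cannot be computed. With assumed standardized effects, same method:

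| Assumed effect on MQS III | Power, 28 per arm | Power, 30 per arm |
|---|---|---|
| 0.5 | 0.43 | 0.46 |
| 0.7 | 0.71 | 0.74 |
| 0.789 | 0.81 | 0.84 |
| 0.9 | 0.90 | 0.92 |

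The stated 0.81 carries over only if the MQS III effect also happens to be about 0.79.

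**Step 3. Effect needed for power 0.80.** This depends on the test and on the shape of the data, so it is a guide only.

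| Test assumption | 28 per arm | 30 per arm |
|---|---|---|
| t-test | 0.762 | 0.736 |
| Mann-Whitney, normal data (3/π) | 0.781 | 0.753 |
| Mann-Whitney, minimum efficiency (0.864) | 0.823 | 0.794 |

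**Step 4. Does 24 versus 48 hours matter?** Assume the same 15 ME difference and SD 19 on each of two days, with between-day correlation ρ (assumed; the documents give none). The 48-hour total then has difference 30 and SD = 19 × √(2(1 + ρ)), from 26.9 at ρ = 0 to 38.0 at ρ = 1. Power at 28 per arm runs from 0.98 down to 0.81. Averaging per 24 hours halves both difference and SD, so power is the same. Under this assumption the change of window does not reduce power.

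**Step 5. Drug scope of the ME inputs.** Within Statistical Power, the background clause refers to opiate requirements, while the clause carrying the 15 ME refers to analgesic use. The recruitment text counts non-opioid classes in ME, but it describes work before the intervention and is not an outcome definition. Neither reading of 47, 15 and 19 ME can be confirmed.

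**The case against.** The strongest defence is that MQS III may simply be the instrument used to score the opiate outcome, and that a collection visit at 48 hours would naturally capture use up to that point. The timing part has force: 48 hours is a scheduled assessment, so the two windows may be the same. The instrument part does not hold on the text. MQS III is attached to analgesic use, no section ties it to opiates or to ME, and the power and final analysis sections use ME and mEQ. The opening pages were not available for review, so a definition there cannot be excluded; the two primary-outcome statements would still differ.

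Several further inferences are tempting but not supported.

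- **That the sample size is wrong or the trial underpowered.** It reproduces on its own scale, and power on MQS III is unknown rather than shown to be low.
- **That opioid-only ME is the scope nearest to the power calculation.** The 15 ME is described as a difference in analgesic use, and the only text on what ME contains covers all analgesics. An all-analgesic reading is at least as literal.
- **That the two outcomes would give different answers.** They might, for instance if opioid use fell while other analgesic use rose. But the documents do not say how MQS III weights drugs, so the extent of any divergence is not shown.
- **That 0.75 or 0.78 is a firm cut-off.** The analysis test itself is not settled: Statistical Analyses in section 3.0 plans mixed models, and section 4.2 plans t or rank-sum tests.

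**Conclusion.** The point stands as an internal inconsistency that must be resolved before unblinding. The plan cannot be followed as written, because two current passages define the primary outcome differently and no rule chooses between them. The stated power of 0.81 applies to ME per 24 hours and does not apply to the section 4.0 outcome, for which no power can be calculated from the documents. Whether it applies to the section 3.0 outcome depends on whether the ME inputs are opioid figures, which is unstated.

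The size of any power loss is unknown. As a guide only, with a Mann-Whitney test and normal data, 60 patients give power 0.80 at a standardized effect of about 0.75, or about 0.78 if 28 per arm are evaluable. Confidence in the inconsistency is high, since it rests on the text and not on assumptions about the data.

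**What to change.** Before unblinding, state one primary outcome, with one drug scope, one measure and one time window. Use it in General Design (section 3.0), Statistical Power, the primary-outcome line of section 4.0, and the Statistical analysis text of section 4.2, where mEQ also needs a definition. Make the drug scope of ME in the recruitment text consistent with it.

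Because the only power inputs are in ME, the simplest route is to replace MQS III in section 4.0 with ME consumption over the first 48 hours after surgery, averaged per 24 hours, using one stated conversion table. The sponsor should then say whether ME is opioid-only, as the General Design text implies, or all-analgesic, and confirm that 47, 15 and 19 ME are on that scope.

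If MQS III is kept as primary, define it. In that case, or if the ME figures turn out to be on a different scope from the chosen outcome, restate the power on the chosen scale.

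The cost is a wording change and possibly a restated power calculation. The edit requires no extra patients or data; section 3.0 already provides for recording medication use. What a restated power would show cannot be judged from the documents.

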#### 2.0 Research significance:

### 2.1 Background

More than 300,000 total knee joint replacement surgeries are performed per year in the United States and safe, effective management of post-operative pain in these patients, often elderly, deconditioned, obese, or with co-morbid diseases like sleep apnea, can be challenging and often require a multidisciplinary, multimodal approach. Opiates have been a mainstay of

treatment in the post-operative period, although continuous epidurals, peripheral nerve infusions of local anesthetic, intra and periarticular injections have all been used in this patient population with varying degrees of success and complications. Inadequately controlled postoperative pain is not uncommon and can cause multiple untoward effects, including a hyperdynamic circulatory state, increased oxygen consumption, muscle spasm of the quadriceps muscles, increased risk of DVT and increased risk of pulmonary embolism, whereas overmedication with opiates can cause hypoventilation syndrome, sedation, pruritus, constipation, or delirium, especially in the elderly population. Further, poorly controlled pain inhibits early mobilization and hinders post-operative physical therapy, both of which are critical in the early post-operative period to prevent joint adhesions, capsular contraction, muscle atrophy, and delays or limitations in the ultimate functional outcome following TKR.

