### Secondary Outcomes include:

- a) Visual Analog Scale for pain: (0 (no pain) to 10 (unbearable pain) scale; at rest, mobilization/ weight bearing.
- b) Knee Society Scale (clinician); WOMAC (patient)
- c) Time to Physical therapy milestones:
  - a. Active SLR
  - b. Time until patient can get out of bed
  - c. Time until patient able to ambulate < 100 feet
  - d. Time until patient able to ambulate around room > 100 feet
  - e. Time until patient is able to climb stairs (quantify specifics, how many steps are considered appropriate?)
- d) Patient Global Perception of Change (GPC)

e) Patient Satisfaction (Likert Scale)

f) Hospital Anxiety and Depression Score (HADS)

- e) SF 12 Questionnaire
- f) McGill Pain Questionnaire
- g) Inpatient length of Stay (LOS; days) and Physical Therapy "clearance for discharge" (days)
- h) Complications of the injection procedure
- i) Medication related adverse effects

A total of 60 patients will be randomized. Participants will complete assessments at these time points:

- 1) Baseline: immediately before the CRFA intervention,
- 2) Immediately prior to surgery (Day of Surgery)
- 3) 48 hours after the surgery procedure
- 4) 1, 3 and 6 months following TKR surgery.

A member of the research team will administer and collect the questionnaires. It will take about 5-10 minutes to complete the questionnaires. The research member will visit the patient at 48 hours to administer the questionnaire and collect data points. It will take approximately 5-10 minutes to complete the questionnaire. In addition, a member of the research team will contact the patient by phone or at scheduled surgical visits at 1 month, 3 months and 6 months.

A member of the research team will look in POWERCHART for physical therapy milestones. Other data points such as medication use, length of stay, time for PT clearance, surgical duration will be recorded. Data collection will be placed on a excel sheet and stored in a pass word protected computer in the department of anesthesiology. Paper data sheets will be placed in a binder and stored in a locked filing cabinet in a locked office located in the department of anesthesiology.

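### The medication-harm outcome is a four-term list that omits two opiate harms the protocol itself names, and its counting window is not stated

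*Combined protocol and SAP*

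**What the plan says.** - **2.1 Background** states that "overmedication with opiates can cause hypoventilation syndrome, sedation, pruritus, constipation, or delirium, especially in the elderly population", and describes knee replacement patients as "often elderly, deconditioned, obese, or with co-morbid diseases like sleep apnea".
- **3.0, Secondary Outcomes, item i** reads in full "Medication related adverse effects". It lists no terms.
- **4.0 Data Analysis, item 11** states the same outcome with terms: "Medication related adverse events (i.e. sedation, nausea, pruritus, delirium". It stands under the heading "Secondary outcomes: Between groups at 48 hours, 1, 3, 6 months in".
- **Contacts after surgery (3.0).** "The research member will visit the patient at 48 hours to administer the questionnaire and collect data points"; later contacts are at "1, 3 and 6 months following TKR surgery". The same section plans to take physical therapy milestones from the electronic record and to record further items. Medication use and length of stay are among its examples; adverse effects are not.
- **Primary outcome (General Design and Procedures):** "post-operative opiate requirements during the first 48 hours after surgery (primary outcome".

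No section defines or grades these harms, or gives their source or look-back period.

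**The concern.** The protocol's account of why opiates are a problem and its list of what will be counted do not agree. An assistant working from item 11 would record four kinds of event. Hypoventilation would not be one of them, although the Background puts it first among the opiate harms and describes patients in whom it is a natural worry. An assistant working from item i could record anything. Neither would know whether an episode on the first night that had cleared by the 48-hour visit should be counted.

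What is at stake is whether safety reporting is complete and uniform. If content and window are settled only after data exist, the tally may differ between assistants or be chosen with results in view.

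**Working it through.** **1. Terms side by side**

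| Harm | 2.1 Background | 4.0, item 11 |
|---|---|---|
| Hypoventilation | named | absent |
| Constipation | named | absent |
| Sedation | named | listed |
| Pruritus | named | listed |
| Delirium | named | listed |
| Nausea | not named | listed |

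The Background has 5 terms and item 11 has 4, with 3 shared. Missing: 2/5 = 40% of the named terms. Added: 1. No other secondary outcome lists either missing harm; complications of the injection procedure are a separate item. The 40% counts terms, not patients or events.

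**2. The two statements of the outcome.** Item i is unrestricted, so it covers both missing harms. Item 11, taken literally, excludes them. Both cannot be followed.

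**3. The window.** The heading in 4.0 gives four times: 48 hours and 1, 3 and 6 months. It also governs times to physical therapy milestones, length of stay, and complications of a procedure done 2-4 weeks before surgery. None of these can be a reading taken at one instant. Section 4.0 also words the primary outcome as a 48-hour value, while General Design makes it cumulative over the 48 hours. The text therefore fits either an instantaneous or a cumulative count of harms and chooses neither.

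To show that the choice matters, assume 20% of 30 controls have a transient event: 30 × 0.20 = 6. If 10% to 75% of these were still present at hour 48, an instantaneous count would find 6 × 0.10 = 0.6 to 6 × 0.75 = 4.5. Both inputs are assumptions. Only the direction is certain: an instantaneous count cannot exceed a cumulative one.

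**4. What 30 per arm can show.** The plan's own figure is 28 per group for the primary outcome (difference 15, SD 19, power .81, two-sided alpha 0.05). The normal approximation, n = 2(z₀.₉₇₅ + z₀.₈₁)² × 19²/15², gives 26. Dividing by the Mann-Whitney efficiency under normality, 3/π = 0.955, gives 27.2, so 28. The figure reproduces. Recruiting 30 allows for 1 − 28/30 = 6.7% loss. That calculation does not address harms.

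For harms, power = Φ{[|p₁ − p₂| − 1.96√(2p̄(1 − p̄)/n)] / √([p₁(1 − p₁) + p₂(1 − p₂)]/n)}, where p̄ is the mean of the two rates and n = 30. The rates are assumed:

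| Control vs C-RFA | Power |
|---|---|
| 5% vs 1% | 0.15 |
| 10% vs 5% | 0.11 |
| 30% vs 15% | 0.28 |
| 40% vs 20% | 0.39 |
| 50% vs 25% | 0.52 |

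The chance of at least one case in an arm is 1 − (1 − p)³⁰: 26%, 45% and 79% for true rates of 1%, 2% and 5%. With no cases in 30, the one-sided 95% upper limit is 1 − 0.05^(1/30) = 9.5%.

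**The case against.** The strongest reply is that this is loose editing. In 4.0 the numbering skips 3 and repeats 6, and a drafting query is left inside the stair-climbing milestone. An *i.e.* written where *e.g.* was meant would fit that pattern, and item i is open. This stands to the extent that nobody can say hypoventilation would certainly go unrecorded. It does not remove the need to reconcile the items, because the only entry with content is the restrictive one.

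A reader might also infer that harms are read as a snapshot at hour 48, so that early events are lost and the harm window fails to match the primary outcome's window. The documents do not support that. The heading has four times and covers outcomes that are not point readings. The researcher collects data points beyond the questionnaire at the 48-hour visit, and the examples of recorded data are an open list. The 5-10 minutes in the design section is questionnaire time, not the length of the visit. The window is unstated; it is not shown to miss events.

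Finally, the small sample means better capture will not yield a useful test. That is correct, and it limits what the fix can claim.

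**Conclusion.** The point holds as a cheap improvement to one secondary outcome. Item 11, read literally, leaves out two of the five opiate harms named in the Background, conflicts with the open wording of item i, and shares with it an unstated window. The omission rests only on taking *i.e.* at its usual meaning. Its size in patients is unknown.

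Two further inferences should be resisted. One is that the trial would miss the main safety gain of opioid sparing. No section calls these harms that; the research question concerns pain scores and analgesic use, and the Significance section does not claim fewer opiate harms. The other is that a fuller list would let the trial show or rule out a difference in hypoventilation. At the assumed rates above, power stays between 0.11 and 0.52. The gain is complete descriptive safety reporting.

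**What to change.** Replace item i in 3.0 and item 11 in 4.0 with one shared text: *any occurrence from end of surgery to 48 hours of hypoventilation/respiratory depression, sedation, nausea, pruritus, constipation, delirium or other medication-related adverse effect*. Add that:

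- the blinded research assistant takes events from the chart review already planned and from the 48-hour visit;
- each term has a brief recording definition, set by the trial team before data collection;
- the number of patients with each event is reported by arm, descriptively, as a stated exception to the mixed-effects analysis that Statistical Analyses applies to all secondary outcomes;
- at 1, 3 and 6 months, new events since the last contact are recorded.

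The cost is the rewording and a few more chart fields per patient. Sample size, visits, treatment and the primary analysis do not change.
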